### 9.4 STATISTICAL ANALYSES

#### 9.4.1 GENERAL APPROACH

The database will be locked after all participants exit the study and all data clarification forms or queries have been resolved. Prior to database lock, a detailed Statistical Analysis Plan (SAP) will be finalized and approved. Final analysis and unmasking of participants' treatment code will occur after database lock.

Wherever appropriate, summary statistics will include the sample size, mean, standard deviation (SD), median, minimum, and maximum for continuous and ordinal variables, and frequency counts and percent for categorical variables. Data will be presented by treatment (0.1% AG-86893, 0.3% AG-86893, AG-86893 vehicle). Additional analyses between vehicle and active drug will be explored, the details of which will be described in the SAP. All testing will be two-sided and will be performed without adjustment for testing multiple measures.

#### 9.4.2 ANALYSIS OF THE PRIMARY EFFICACY ENDPOINT

The primary efficacy measure is overall conjunctival hyperemia score of the study eye using the average of the scores of each quadrant, as assessed by the reading center. The primary endpoint is the change from baseline in overall conjunctival hyperemia score at Day 28, so scores from Days 1 and 28 will be analyzed. The primary efficacy analysis will be based on the mITT population. Refer to the MOP for details on the collection of ocular photography.

Statistical analyses will be performed as described in [Section 9.4.1](#) for continuous variables.

---

#### 9.4.3 ANALYSIS OF THE SECONDARY ENDPOINTS

Secondary endpoints include:

- Change from baseline in overall conjunctival hyperemia score at Day 7
- Change from baseline in conjunctival hyperemia score in the quadrant with the pterygium at Days 7 and 28
- Concentration of AG-86893 in plasma over time

Statistical analyses will be performed as described in [Section 9.3](#) for continuous and categorical variables.

---

#### 9.4.4 SAFETY ANALYSES

All safety analyses will be conducted on the safety population using the following safety variables:

- Adverse events
- Concomitant medications
- Concurrent procedures
- Vital signs
- Laboratory tests (urinalysis, hematology, and serum chemistry parameters)
- Electrocardiogram
- Best-corrected visual acuity
- Intraocular pressure using a Goldmann applanation tonometer
- Biomicroscopy
- Tear film break-up time
- Lissamine green conjunctival staining
- Ophthalmoscopy

The Medical Dictionary for Regulatory Activities (MedDRA) nomenclature will be used to code AEs. For each AE reported, the number and percent of participants will be tabulated based on the preferred term. The tables will be generated by relationship to treatment as well as by system organ class and severity. Treatment-emergent AEs will be considered, as will AEs occurring prior to first dose and post-treatment.

---

#### 9.4.5 BASELINE DESCRIPTIVE STATISTICS

Baseline and demographic assessments will be presented descriptively.

---

#### 9.4.6 PLANNED INTERIM ANALYSES

No interim analyses are planned.

---

#### 9.4.7 SUBGROUP ANALYSES

No subgroup analyses are planned.

---

#### 9.4.8 TABULATION OF INDIVIDUAL PARTICIPANT DATA

Line listings will be provided for each participant.

---

#### 9.4.9 EXPLORATORY ANALYSES

Exploratory endpoints include:

- Pterygium vascularity scores at Days 1, 7, and 28 visits
- Pterygium volume at Days 1, 7, and 28 visits
- Pterygium vessel length at Days 1, 7, 28, and 56 visits

---

#### 9.4.10 PHARMACOKINETIC ANALYSIS

The plasma AG-86893 concentrations will be summarized for each dose for the Days 1 and 28 visits.

A model-independent approach will be used to calculate plasma PK parameters for AG-86893, including  $AUC_{0-t}$ , and  $C_{max}$ , whenever possible.

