3.4 Randomization and Masking

Eligible participants will be assigned in 1:1:1 ratio into 1 of the 3 treatment groups. A central randomization scheme will be prepared by an unmasked Trial Runners representative and dispensed via an Interactive Web Response System (IWRS). Randomization schedule will be optimized as much as possible to achieve a balanced distribution of treatment assignment by investigational site, baseline hyperemia severity (grade of 2 vs. > 2), and PK participation.

Randomization assignment will occur by site personnel via IWRS once a participant's eligibility is determined by the investigator and confirmed by the central reading center. The IWRS will provide a unique Subject ID to be used in all study documents as the study identifier.

Study drug will be labeled with medication kit numbers, and the IWRS will provide each site with the specific medication kit number(s) for each randomized participant at the time of randomization. Sites will dispense study drug according to the IWRS instructions. Sites will receive the IWRS confirmation notifications for each transaction. All notifications are to be maintained with the study source documents.

Treatment assignment will be masked to the study participants, the investigators, all study-site personnel (with the exception of the unmasked drug administrator), study monitoring personnel, as well as Central Reading Center personnel during the entirety of the study. Day 28 efficacy and safety results based on the 1st database lock will be presented with unmasked treatment group, but no disclosure of treatment assignment at individual participant level.

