Participant level listing will be provided with related information that include AE onset/resolution date, study days, duration, preferred terms, relationship to study eye drop, action taken, outcome, and sorted by treatment, subject ID and onset date.

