6.7 Pharmacokinetic Analyses (if data available)

Pharmacokinetic analysis, if applicable, will be based on the PK sub-population using a model-independent approach.

Drug plasma concentration data will be summarized for each dose by descriptive statistics using SAS®. AUC_{0-1h} will be estimated using linear trapezoidal method.

Individual and mean concentration at each time point, C_{max} , T_{max} , and AUC_{0-1h} , where applicable, will be presented by treatment group for Day 1 and Day 28. On Day 56 individual and mean \pm SD will be presented.

Individual and mean concentration-time curves will be presented for Day 1, and Day 28 to illustrate the dynamic change of plasma concentration from hour 0 to 1.

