8 INTERIM ANALYSES

No interim analysis for efficacy is planned for this study.

Two database locks are scheduled for this study. The first database lock will occur after all participants completed the Day 28 visit for the primary efficacy analysis (including grading by the central reading center), localized pterygium conjunctival hyperemia, PK analysis (if applicable), and summary of safety data gathered up-to-date. The final lock will occur at study completion (Day 84) for longer term assessment of safety, tolerability, treatment effect, and plasma concentrations monitoring of AG-86893 (if applicable). Eligibility for analysis will be determined prior to each database lock.

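### The SAP puts individual PK displays in the Day 28 lock without a safeguard that keeps individual assignments masked until the final lock

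*Protocol*

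**What the plan says.** SAP 8 schedules two locks. The first follows completion of Day 28 by all participants. It covers the primary efficacy analysis with central grading, localized hyperemia, "PK analysis (if applicable), and summary of safety data gathered up-to-date". The final lock comes at study completion (Day 84). Eligibility for analysis is set before each lock.

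SAP 6.7 defines the PK output. "Individual and mean concentration at each time point" is shown by treatment group for Days 1 and 28, together with Cmax, Tmax and AUC over the first hour. In addition, "Individual and mean concentration-time curves will be presented for Day 1, and Day 28". SAP 7.5 refers to a concentration listing, and SAP 7.4 orders participant listings by participant number. Neither section says at which lock the listing is issued.

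On masking, SAP 3.4 says that Day 28 efficacy and safety results from the first lock "will be presented with unmasked treatment group, but no disclosure of treatment assignment at individual participant level". Protocol 6.3 keeps individual assignments masked until the database is locked for the final analysis. Protocol 4.1 and 9.4.1 place locking and unmasking after all participants have exited.

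Protocol 9.4.10 summarizes by dose ("The plasma AG-86893 concentrations will be summarized for each dose for the Days 1 and 28 visits") and also plans parameters: "A model-independent approach will be used to calculate plasma PK parameters for AG-86893". Protocol 9.4.8 adds: "Line listings will be provided for each participant".

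**The concern.** SAP 3.4 lets group results be seen early on condition that no individual's arm is revealed. SAP 6.7 and 8, followed as written, allow individual PK values to be shown under a treatment heading at that same lock.

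PK data are also unusually revealing. Protocol 6.2.2 shows that vehicle contains no AG-86893, so a measurable post-dose concentration against a participant number points to active drug even without a treatment label.

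The stake is what is still open after the first lock. Day 56 and Day 84 adverse events may still need a causality judgement, queries may remain, and eligibility is decided again for the final lock. Knowing individual arms could colour those decisions.

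**Working it through.** The plan gives no figure to reproduce. The check sets the sections side by side and then bounds the number of participants involved.

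**1. Do the outputs fit the safeguard?**

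| Question | What the documents give |
|---|---|
| Is PK in the first lock? | Yes, if applicable (SAP 8) |
| Does the PK analysis include individual values by group? | Yes (SAP 6.7) |
| Are individual displays deferred to the final lock? | Not stated |
| Are they de-identified? | Not stated |
| Who receives first-lock output? | Not stated |
| Does the no-disclosure rule cover PK? | Not named (SAP 3.4) |
| Is PK exempt from individual masking? | No exception given (Protocol 6.3) |

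**2. When does an individual value disclose an arm?**

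- No PK data at the first lock, or values by group with no identifier and no linkable listing: no disclosure from the output alone.
- Values against participant numbers, without a treatment label: a measurable post-dose value shows active versus vehicle, but not 0.1% versus 0.3%. A value below the limit of quantification (target 0.020 ng/mL) does not prove vehicle, because SAP 7.5 expects low concentrations.
- Values against participant numbers under a group heading: the exact arm is disclosed.
- Unlabelled values by group, together with a listing ordered by participant number: the two can be matched by value. Sampling gives up to five values after the first dose by Day 28 (two on Day 1, three on Day 28), so profiles with measurable values would usually be distinguishable. Profiles entirely below the limit cannot be matched this way.

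**3. How many participants?**

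- Planned PK subset (SAP 3.1.5): 6 × 3 = 18, of whom 6 × 2 = 12 are on active drug. Protocol 8.2 says at least 6 per group, so the subset could be larger.
- Share of planned enrolment: 18/70 = 25.7%.
- Range: 0 up to all PK participants with first-lock data.
- SAP 5.5 requires all blood samples. Read literally, this includes Day 56, so PK participants without that sample would not yet be in the PK population.

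**4. How many would still be in follow-up?**

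The gap from Day 28 to Day 84 is 56 days, or 8 weeks. Assume even accrual over 52 to 78 weeks and a lock promptly after the last Day 28 visit. The documents give only an 18-month study duration.

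- All participants: 70 × 8/78 = 7.2 to 70 × 8/52 = 10.8.
- PK subset: 18 × 8/78 = 1.8 to 18 × 8/52 = 2.8.
- PK subset without a Day 56 sample (4-week gap): 18 × 4/78 = 0.9 to 18 × 4/52 = 1.4.

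If the lock comes 8 weeks or more after the last Day 28 visit, nobody is still in follow-up. Coding, deviation and eligibility decisions could still be open until the final lock.

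**5. What is not affected?**

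SAP 8 requires central grading before the first lock, and eligibility for that lock is set beforehand. The Day 28 primary endpoint is therefore fixed before any PK output exists.

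**The case against.** The case against is substantial, and most of it narrows the point.

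- **SAP 3.4 names efficacy and safety results, not PK, and bars disclosure of assignment, not of data values.** This stands as a reading of the sentence. It means that the most revealing first-lock output has no stated rule, while Protocol 6.3 makes no exception for PK.
- **Disclosure needs an identifier.** This stands. SAP 6.7 specifies none, and the concentration listing is not assigned to a lock. But nothing de-identifies or delays these outputs, and the listing convention in SAP 7.4 supplies participant numbers.
- **The people who make the judgements remain masked.** SAP 3.4 keeps investigators, site staff other than the drug administrator, monitoring personnel and the reading center masked throughout. This weakens the route to bias. It does not close it, because the recipients of first-lock output are not named.
- **PK is conditional throughout the SAP.** This stands, and it is why the range starts at 0.

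A reader might also infer that the Protocol plans only dose-level summaries and that the SAP departs from it. The documents do not support this: Protocol 9.4.8 plans participant listings with no exception for PK, and 9.4.10 itself goes on to PK parameters.

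A reader might likewise take the adverse event listing in SAP 6.6.1, "sorted by treatment, subject ID and onset date", as a second disclosure. SAP 8 promises only a summary of safety data at the first lock, so that listing matters only if it is issued then. What is certain is that its sort order differs from SAP 7.4.

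**Conclusion.** The point holds as a minor one. SAP 6.7 and 8 permit individual PK displays by treatment group at the Day 28 lock, and no text reconciles this with SAP 3.4 or with Protocol 6.3. If the values carry or can be linked to participant numbers, assignment (at least active versus vehicle) can be disclosed for between 0 and all PK participants with first-lock data, with 18 of 70 (26%) as the ceiling at 6 per arm.

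It would be too strong to say that the masking promise is broken for every PK participant. That would require PK data to exist at the first lock, an identifier or a linkable listing to be released with them, and every profile to be informative. The documents establish none of these. The figure of about 2 to 3 PK participants still in follow-up depends on the assumed accrual and a prompt lock.

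The primary endpoint is not at risk. What remains exposed is adverse event causality at Days 56 and 84, and eligibility for the final lock.

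**What to change.** In SAP 3.4, 6.7 and 8:

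- Extend the rule against individual disclosure at the first lock to PK results.
- Limit first-lock PK output to group-level summaries: n, number below the limit of quantification, mean, SD and order statistics.
- Hold individual concentrations and parameters, individual curves, the concentration listing and any treatment-sorted participant listing until the final lock. With 6 per group, a minimum or maximum is itself one participant's value, so withholding the listing matters as much as dropping the individual displays.
- Name who receives first-lock output.
- Bring the sort order in SAP 6.6.1 into line with SAP 7.4.

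The cost is a few sentences in the SAP, with no change to visits, sample size or the primary analysis. The downside is that individual PK profiles reach the project team at the final lock instead of the first. If they are needed sooner, they could go under scrambled identifiers to a pharmacokineticist kept separate from the study team.

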## 10 SUPPORTING DOCUMENTATION AND OPERATIONAL CONSIDERATIONS

### 10.1 REGULATORY, ETHICAL, AND STUDY OVERSIGHT CONSIDERATIONS

---

#### 10.1.1 INFORMED CONSENT PROCESS

##### 10.1.1.1 CONSENT AND OTHER INFORMATIONAL DOCUMENTS PROVIDED TO PARTICIPANTS

Consent forms describing in detail the study intervention, study procedures, and risks, that have been reviewed and approved by the relevant HREC/IRB/IEC, will be given to the participant and written documentation of informed consent will be required prior to starting study intervention.

##### 10.1.1.2 CONSENT PROCEDURES AND DOCUMENTATION

The study will be discussed with the participant, and each participant wishing to participate must give written informed consent prior to enrollment into the study and prior to any study-related procedures or change in treatment.

Each participant who provides informed consent will be assigned a participant number by the IVRS/IWRS that will be used on participant documentation throughout the study.

---

#### 10.1.2 STUDY DISCONTINUATION AND CLOSURE

The study may be stopped at the participant's study site at any time by the site investigator. Allgenesis may stop the study (and/or the study site) for any reason with appropriate notification.

---

#### 10.1.3 CONFIDENTIALITY AND PRIVACY

A report of the results of this study may be published or sent to the appropriate health authorities in any country in which the study drug may ultimately be marketed, but the participant's name will not be disclosed in these documents. The participant's name may be disclosed to Allgenesis, the governing health authorities, or the US Food and Drug Administration or the Therapeutic Goods Administration if they inspect the study records as required by law. Appropriate precautions will be taken to maintain confidentiality of medical records and personal information.

Every precaution must be taken to protect the privacy of research participants and the confidentiality of their personal information in accordance with the Australian Privacy Act 1988.

In accordance with Health Insurance Portability and Accountability Act Standards for Privacy of Individually Identifiable Health Information (HIPAA) requirements, additional purposes of this study include (1) the publishing of anonymous participant data from the study, and (2) the creation and maintenance of a data repository.

All study-related correspondence, participant records (i.e., source documents listed in Section 11.4.1), ICFs, participant privacy documentation, records of the distribution and use of all investigational products, and participant questionnaires, correspondence with HREC/IRB/IEC, and other essential documents should be maintained on file.

Local regulatory requirements should be followed regarding the retention of clinical study documentation (TGA requires retention for at least 15 years after study completion; the Sponsor will advise once documents can be destroyed).

Allgenesis requires that it be notified in writing if the investigator wishes to relinquish ownership of the data so that mutually agreed-upon arrangements can be made for transfer of ownership to a suitably qualified, responsible person.

---

#### 10.1.4 FUTURE USE OF STORED SPECIMENS AND DATA

Not applicable.

---

#### 10.1.6 SAFETY OVERSIGHT

Should there be any findings of concern that warrant further investigation, the Medical Monitor will convene a meeting of the IDMC to determine whether any changes in the study conduct should be made. Targeted AEs / findings of interest are summarised in section 8.3.11 and described in detail in the IDMC Charter, along with the qualifications for the independent safety experts.

---

#### 10.1.7 CLINICAL MONITORING

Clinical site monitoring is conducted to ensure that the rights and well-being of trial participants are protected, that the reported trial data are accurate, complete, and verifiable, and that the conduct of the trial is in compliance with the currently approved protocol/amendment(s), with ICH Good Clinical Practice (GCP), and with applicable regulatory requirement(s).

- A representative of Allgenesis will monitor the study on a periodic basis. The determination of the extent and nature of monitoring will be based on considerations, such as the objective, purpose, design, complexity, masking, size, and endpoints of the study
- Authorized representatives of Allgenesis or regulatory authority representatives will conduct on-site visits to review, audit, and copy study-related documents. These representatives will meet with the investigator(s) and appropriate staff at mutually convenient times to discuss study-related data and questions

---

#### 10.1.8 QUALITY ASSURANCE AND QUALITY CONTROL

Each clinical site will perform internal quality management of study conduct, data and biological specimen collection, documentation, and completion.

Quality control (QC) procedures will be implemented beginning with the data entry system and data QC checks that will be run on the database will be generated. Any missing data or data anomalies will be communicated to the site(s) for clarification/resolution.

Following written Standard Operating Procedures, the monitors will verify that the clinical trial is conducted and data are generated and biological specimens are collected, documented (recorded), and reported in compliance with the protocol, ICH GCP, and applicable regulatory requirements (e.g., GLP, Good Manufacturing Practice).

The investigational site will provide direct access to all trial-related sites, source data/documents, and reports for the purpose of monitoring and auditing by the sponsor, and inspection by local and regulatory authorities.

---

#### 10.1.9 DATA HANDLING AND RECORD KEEPING

##### 10.1.9.1 DATA COLLECTION AND MANAGEMENT RESPONSIBILITIES

This study is to be conducted in compliance with the regulations on electronic records and electronic signature.

Data collection is the responsibility of the clinical trial staff at the site under the supervision of the site investigator. The investigator is responsible for ensuring that data are properly recorded on each participant's eCRFs and related documents in a timely manner. An investigator who has signed the protocol signature page should electronically sign the eCRFs to ensure that the observations and findings are recorded on the eCRFs correctly and completely. All source documents should be completed in a neat, legible manner to ensure accurate interpretation of data.

- Clinical data will be entered into eCRFs. Data entered into the eCRF will correspond with and be supported by source documentation maintained at the site(s). A final report of all participant data will be provided to each site at the end of the study to serve as eCRF documentation
- Blood chemistry panel, hematology, and urinalysis will be analyzed at a central clinical laboratory
- Electrocardiogram data will be collected and provided to a centralized reading center for analysis and interpretation, including eligibility for study entry. A final report of all participant ECG data will be provided to each site at the end of the study to serve as ECG documentation
- IVRS/IWRS will be used for randomizing the participant population

- Images for conjunctival hyperemia/pterygium vascularity scoring, and AS-OCT lesion volume data will be collected and provided to a centralized reading center for analysis and interpretation, including eligibility for study entry. A report of all participant hyperemia/vascularity data and lesion volume will be provided to each site
- Plasma drug concentration samples will be analyzed using validated assays to measure drug concentrations

Source documents may include a participant's medical records, diaries, hospital charts, clinic charts, the investigator's participant study files, as well as the results of diagnostic tests, such as x-rays, laboratory tests, and ECGs. The investigator's copy of the eCRFs serves as part of the investigator's record of a participant's study-related data.

The following information should be entered into the participant's medical record:

- Participant's name
- Participant's contact information
- Date that the participant entered the study, participant number, and participant medication kit number
- Study title and/or the protocol number of the study and the name of Allgenis
- Statement that informed consent was obtained (including the date) prior to any study procedures being performed and that the participant was provided a copy of the signed informed consent. A statement that country and local participant privacy-required documentation for this study has been obtained (including the date)
- Dates of all participant visits
- All concurrent medications (List all prescription and non-prescription medications being taken at the time of enrollment. At each subsequent visit, changes to the list of medications should be recorded.)
- Occurrence and status of any AEs (including any procedure-related AEs)
- The date the participant exited the study, and a notation as to whether the participant completed the study or reason for discontinuation
- The results of laboratory tests performed by the central laboratory (hematology, serum chemistry, urine analysis, urine culture and sensitivity)
- The results of laboratory tests performed by the site (e.g., urine pregnancy test)
- The results, if applicable, of any procedures performed to confirm eligibility criteria
- Concurrent procedures performed during the study
- Documentation of the participant's medical history
- Vital signs and physical characteristics (height and weight)
- Electrocardiogram traces
- Results of biomicroscopy/ophthalmoscopy exams
- Documentation of whether any procedure, including study treatment administration, was performed according to the protocol, noting any deviations (if applicable)
- Study drug accountability and reconstitution records (stored separately with the accountability logs in order to maintain masking status for site staff with direct contact with participant and/or data)

